6.2. Secondary outcome measures

Secondary outcomes include:

- Sellers' verbally inquiring about buyer age
- Sellers' requesting ID cards from buyers for age verification
- Sellers' dissuading buyers from using e-cigarettes (added after the pilot study)

6.3. Other outcome measures

Other outcome measures primarily include:

- Illegal flavored products being sold

The simulated buyers will report if sellers mention that flavored (not allowed in China) e-cigarette products are available in the stores.

- Online contact

The simulated buyers will report if WeChat account information is publicly displayed for adding contacts.

- Delivery service offered

The simulated buyers will report if sellers mention that products ordered online can be delivered to them.

- Marketing claims

The simulated buyers will record the marketing claims of sellers to promote the products

6.4. Design of the assessing tool

The assessing tool will be used by simulated buyers to check whether all information is

recorded after leaving the store, and all data will be inputted.

The assessing tool is designed primarily based on the Vape Shops Standardized Tobacco Assessment for Retail Setting (V-STARS)²² and Tobacco Advertising, Promotion and Sponsorship (TAPS) bans compliance guide²³, and published articles¹⁴. It will be further adapted by investigators who are familiar with Chinese e-cigarette retailers and laws and have observed store characteristics, to the Chinese context to collect information mainly on store internal/external environmental features (e.g., location, advertising, warning signs, and licensing), product availability, and seller behaviors.

After the initial version of the assessing tool is finished, a pilot investigation will be conducted to further revise and finalize this instrument. The pilot trial will be conducted by two simulated buyers (18-19 years old, see the requirements in Section 7.3), accompanied with coordinators, in 2 metropolitan areas: Beijing and Shijiazhuang (the capital city of Hebei Province). Each simulated buyer will conduct mystery shopping and point-of-sale auditing in 10 e-cigarette stores. After data collection is complete for each store, coordinators will discuss with simulated buyers encountered problems and possible solutions, as well as further refine the research process and assessing tool. Detailed information can be seen in Section 7.2. The final assessing tool can be seen in Appendix 4.

7. Study procedures

The trial will be registered at ClinicalTrials.gov, and will be conducted after getting permission or exemption from the ethical review from Peking University Institutional Review Board (IRB).

7.1. Subject enrollment and randomization

7.1.1. Screening and enrollment

First, after obtaining a list of e-cigarette stores through keyword searching, we will remove e-cigarette stores without contact information based on the eligibility criteria. Stores not located in main districts of the metropolitan areas (see Appendix 2) will be then removed with Excel filter function, and investigators will further manually delete those that are judged to be non-e-cigarette shops. In this way, a pool for the sampling of trial subjects will be generated.

Second, using R software, each store will be assigned a random number and all the stores in the list will be ordered by the random number from smallest to largest, so that each store with a phone number will have an equal probability of being enrolled in this study. Subsequently, as each selected store needs to be contacted for confirming their opening, this trial will further exclude those stores which have the same contact information as the other store. If more than one store with the same telephone number exists, only the first one will be kept.

Finally, e-cigarette retailers will be called in the ascending order of random numbers for inquiring about their operating status and verifying that their address is correct, until 40 stores are confirmed to be still in business for each metropolitan area (if the number allows). A telephone protocol (Appendix 5) will be used to standardize communication process to collect relevant information. Callers will pretend to be potential buyers who may be visiting the store shortly, and each store will be contacted once again on the second day if not answered.

7.1.2. Informed consent

This study uses the mystery shopping approach and all the e-cigarette store owners and sellers will not be informed that they are enrolled in this trial.²⁴⁻²⁶

7.1.3. Randomization

Prior to the randomization of subjects, all the eligibility criteria must be met.

- **Generating clusters to which the stores belong:** Considering traveling time and the efficiency of data collection, this trial will use a cluster randomization approach, rather than simple randomization. Investigators will firstly map all the 40 selected stores within each metropolitan area, then divide them into clusters that contains the same number (usually 4 stores) considering their locations and public transportation. Then each cluster will be digitally labeled, from area 1 to area 8. The labeling of the clusters follows the principle of from top to bottom, from left to right on the map.
- **Assigning clusters to treatment:** Each cluster will be randomly assigned to one simulated buyer, and the attire (school uniforms or casual attire) he/she wears on a specific day will also be random. In this way, the e-cigarette stores will finally be allocated at a 1:1 ratio to either the intervention or control group.
 - (1) Specifically, the simulated buyers (data collectors) to be recruited are 18 to 19 years old, with a 1:1 ratio of males to females. To reduce bias associated with personal characteristics of simulated buyers, they will be randomly assigned a new digital number for each metropolitan area, which is used for matching the clusters.
 - (2) The type of attire wore by each adolescent on a specific day will be pre-determined using the Excel's random number generator within each sex, and each adolescent will have an equal probability to wear school uniforms and casual attire during the entire study.

7.1.4. Blinding

It will be impossible to blind study subjects regarding the assignment to the intervention or control group, as letting sellers in the e-cigarette stores see the buyers' attire is part of the treatment. However, sellers will not be aware of the participation in this trial because of the mystery shopping approach adopted.

The trial team, consisting of both data collectors and coordinators collecting outcomes, will also not be blind to e-cigarette stores in the intervention and control groups, because there is no way to not let them know the e-cigarette stores with simulated buyers with school uniforms or casual attire on each day.

The statistician conducting analyses will have no direct contact with e-cigarette stores but will not be blind to the treatment allocation.

7.2. Pilot study

Aim: To refine the treatment procedures and improve the assessing tools

Subjects: 20 e-cigarette stores, including 10 in Beijing and 10 in Shijiazhuang (the capital city in Hebei Province). These 20 e-cigarette stores will be selected from the list we complied, and will not be revisited in the formal trial.

Time: After subject enrollment but prior to data collector training

Data collectors (simulated buyers): two adolescents aged 18 or 19 years old, including one male college student and one female college student. The requirements for them are same as the that for the formal trial. For each adolescent, a coordinator will accompany him/her for any necessary help and further discussion for the treatment procedures.

Treatment: 10 stores will receive an adolescent buyer wearing casual attire and the other 10 stores will receive a simulated buyer wearing school uniforms. All the treatment procedures will be same as the formal trial, which can be seen in **Section 5**.

Evaluation after the pilot trial: After the data collection of 20 polit e-cigarette stores, the research team will discuss the problems encountered and possible solutions with each simulated buyer, as well as further refine the research process and the assessing tool.

7.3. Data collector recruitment

We plan to recruit 25 college students in Beijing through social media in June-July 2023, including 12 males and 13 females, where the one additional female data collector will be recruited considering that females may need to take some days off during the fieldwork due to health-related reasons. This way, a gender-balanced sample will be more likely to be achieved.

Requirements including:

- Aged 18 or 19 years old (according to the WHO standard, adolescents are defined to less than 20 years old)
- Having never used any tobacco products including e-cigarettes and cigarettes

- No apparent dyed hair
- No tattoos being seen

A poster will be designed and posted in WeChat Moments and online forums to recruit the simulated buyers in Beijing. It also will be shared among faculty, staff, and students at several universities in Beijing. The poster will contain the following information, including study title, location, time of the investigation, requirements, compensation, and contact information. Considering the need to keep the study confidential from Chinese e-cigarette retailers, the investigators will avoid mentioning too many details in the recruitment poster and only inform adolescents of more specific information in the subsequent interview sessions.

The coordinator will create a WeChat group of the adolescents who sign up. In July 2023, an online interview will be performed to communicate with those who are willing to take part in, providing them with more details about the trial, and check whether they are eligible for the investigation.

Each simulated buyer will receive CNY 350 (approximately USD 50) per day as payment and all accommodation and transportation costs will be covered by the study.

7.4. Training data collectors

7.4.1. Course Training

After recruiting the adolescents participating in the trial, the investigators will arrange a one-day on-site training. The training will be conducted in the form of PowerPoint presentations and lectures by investigators and coordinators. The training date is set within seven days prior to the formal investigation.

The training content will include the study background, purpose, process, time schedule, precautions in the fieldwork, etc. Investigators will make sure that simulated buyers understand the roles they play. Coordinators will show them the pictures of retail stores, product advertisements, and warning signs to help them quickly and accurately identify the details they need to record in the study. At the end of the lecture, the coordinator will role-play the seller in one (or more) simulated interactions with simulated buyers to help them better perform in real-life possible scenarios.

An investigation manual will be provided by the coordinator to the simulated buyers to guide them in the proper conduction of the survey and completion of the questionnaire. The manual will include training contents, detailed explanations of the questionnaire items, special situations handling strategies, and how to communicate with sellers in a standardized manner (without making them suspicious).

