2.1. Hypothesis

We hypothesize that dressing in school uniforms (compared to casual attire)* by adolescents will significantly increase the likelihood of e-cigarette sellers verifying the age of buyers in stores and reduce the probability of their illegal sales to minors.

The corresponding null hypothesis that will be tested is that dressing by school uniforms by adolescents will have no effect upon e-cigarette selling behaviors in regulation compliance.

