5.1. Treatment and control

Each e-cigarette store will be visited by a simulated buyer (also serving the role of a data collector) who aged 18-19 years old and wear a certain type of attire, including carried accessories. If necessary, the buyers will claim that (1) they are adults but will not show any age proof; (2) they have never tried any tobacco products; (3) they want to buy e-cigarettes out of curiosity because their friends are using the products.

The sellers' behaviors and claims will be documented immediately after the simulated buyers leave the stores. The primary difference between the treatment group and control group is the attire that buyers wear: school uniforms vs. casual attire.

Treatment group: The e-cigarette stores will receive a simulated buyer of a randomly assigned sex who will wear a school uniform, carry a school bag, and attempt to purchase e-cigarette products.

Control group: The e-cigarette stores will receive a simulated buyer of a randomly assigned sex who will wear casual attire, carry a business style bag (backpacks for males and handbags for females), and attempt to purchase e-cigarette products.

1:1 matching: After mystery shopping and point-of-sale auditing in an e-cigarette store, simulated buyers will search for the nearest store where traditional cigarettes can be purchased and conduct a similar visit intervention.

Note: The simulated adolescent buyer (also the data collector) will role-play a minor under 18 years old who attempt to buy e-cigarettes. Only adolescents aged 18 or 19 years old will be recruited in this study because it is theoretically difficult to distinguish whether they are under or above 18 years old from the facial features. This trial will not recruit minors who are younger than 18 years old because it is illegal for them to purchase e-cigarette products in China.

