10.3. Follow-up processing

For the purchased e-cigarette and cigarette products, some will be given to scientific research institutions for academic purposes, and others will be sent to tobacco control associations as samples for educational purposes.

11. Data processing and storage

The data will be collected through the self-developed instrument embedded in the Questionnaire Star platform (an App on smart phones), downloaded by the investigators at the end of the survey and saved on the principal investigator's computer located in the office. Statisticians will create the database in a timely manner, and the data will then be backed up and locked with passwords by investigators and research assistants after it has been thoroughly reviewed. To ensure data security, a non-permitted person cannot modify the data. All related analyses will be conducted on the principal investigator's computer. Staff who have access to the information of the trial subjects will sign confidentiality agreements. All the data in the study will be available to principal investigators, who have ultimate authority for the decision on data. The information shall not be disclosed to any third party (other than persons or institutions directly involved or required to know by law) without the prior consent of principal investigators. The investigators must take all appropriate precautions to avoid disclosing the information to third parties or the public by any staff or institutions.

12. Study Timeline

We plan to complete the preliminary recruitment of adolescents who will work as simulated buyers and data collectors, store sampling, and pilot survey from June 2023 to July 2023. In July 2023, we will train the simulated buyers and conduct the randomization of simulated buyers and e-cigarette stores. From July 2023 to September 2023, we will divide the data collectors into three teams and carry out the trial investigation. Data cleaning and analysis will be conducted after September 2023.

13. Role of funding source

This study is funded by the China Medical Board in the United States. The funder will have no role in the study design, data collection, analysis, interpretation, or writing of the paper.

14. Declaration of interests

There are no financial or other competing interests for the principal investigators in the overall trial or at each study site.

15. Reference

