- If a seller offers you to try an e-cigarette, they usually provide a disposable tool. Respond with, "This seems unsanitary, I won't use it... I'd rather buy a new one/I'd rather use my friend's."
- The seller might claim that the e-cigarette and cartridges are sold as a set, and that a friend's e-cigarette might not be compatible. You should insist on only buying the cartridges, "It's fine, I remember it's just like this one/... just buy a box of these."

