Appendix 6 Recruitment poster for simulated buyers

The China Center for Health Development Studies at Peking University will conduct a survey on the behaviors and marketing strategies of e-cigarette retail stores in several major metropolitan areas in China. The survey is expected to begin from July 22-25 and last for about three weeks. Offline training will be provided before the official start date. Scan the QR code to sign up, and you will gain valuable research experience and generous compensation. This is also a great opportunity to visit various places in China and explore local delicacies.

Recruitment Criteria:

University students aged 18 or 19 currently studying in Beijing.

Have never used cigarettes or e-cigarettes.

Possess good communication skills and a sense of responsibility, and can commit to the training and the entire survey period.

Benefits:

Accommodation and transportation fees covered, with a daily compensation of CNY 350.

Outstanding researchers have a chance to receive a surprise gift pack!

After the survey, the research team will verify the quality of the questionnaires and issue a certificate of practice.

QR Code for Registration:

We sincerely look forward to your participation! If you have any questions, feel free to contact us via phone or WeChat: [name].

>>>>>>>>> 暑期调研员
招募

JOIN US

加入
我们

扫码报名，

收获宝贵的科研实践经历+丰厚报酬，
一次游览祖国多地、探索特色美食的绝佳机会！

北京大学中国卫生发展研究中心将对我国多个重
要城市电子烟零售店的环境及营销策略进行调查，
预计7月22-25日开始，为期约3周，将于正式开始
前2日进行线下培训。

● 招募条件

1. 北京在校的18、19岁大学生；
2. 从未使用过香烟和电子烟；
3. 具备良好沟通能力和责任心，能全程参与培训及调研。

● 福利

1. 包住宿和交通费，劳务费每天350元及以上。
优秀调研员有机会获得**惊喜大礼包**哦！
2. 调研结束后，课题组将核实问卷质量后开具实践证明。

真诚期待您的参与！如有疑问，欢迎电话或微信咨询：

[name]

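### Unblinded buyers run each visit and alone record it, with no stated limit on persisting after a refusal and no check of recorded sales, so expectation could act by arm

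*Protocol*

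**What the plan says.** Protocol 5.1 and 7.6 give one person three tasks: the simulated buyer wears the assigned attire, conducts the purchase attempt, and completes the phone questionnaire after leaving the store. Section 7.1.4 states: "The trial team, consisting of both data collectors and coordinators collecting outcomes, will also not be blind to e-cigarette stores". Section 7.4.1 describes the course given to these buyers: "The training content will include the study background, purpose, process, time schedule, precautions in the fieldwork, etc". The hypothesis in Section 2.1 is directional, namely that uniforms "will significantly increase the likelihood of e-cigarette sellers verifying the age of buyers in stores and reduce the probability of their illegal sales to minors", and the rationale in Section 1.2 points the same way.

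Section 5.2 relies on a soft script, printed in Appendix 2. It suggests phrases, tells the buyer how to press on price, and under special situations adds one firm instruction: "You should insist on only buying the cartridges". Section 7.4.1 also provides role-play and a manual. Section 7.4.2 requires more than 90% of objective questionnaire items to be correct before a buyer is released to the field.

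Purchased products are kept. Section 10.3 says only where they go: "For the purchased e-cigarette and cigarette products, some will be given to scientific research institutions for academic purposes", with the rest sent to tobacco control associations. The recruitment poster in Appendix 6 is neutral: it says the centre will "conduct a survey on the behaviors and marketing strategies of e-cigarette retail stores" and does not mention attire.

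**The concern.** The buyers cannot be blinded to what they wear. Three other things are choices: what they are told about the aim, how much latitude they have when a seller resists, and whether anyone checks what they report.

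A buyer who expects to be refused in uniform may give up after the first hesitation, yet ask again in casual clothes. That changes the encounter itself, and so the true sale rate in each arm. The same buyer may also be readier to score a remark as dissuasion, or a cool reception as being asked to leave. Randomisation does not remove either effect, because both arise after allocation and follow the attire. Each buyer works in both attires (Section 7.1.3), which balances fixed traits such as looks or confidence but not an expectation tied to the clothing. A larger sample would only estimate the shifted difference more precisely.

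**Working it through.** **1. The plan's own figure.** Protocol 8.6 and SAP 1.4 give two-sided alpha 0.05, power 0.85, cluster size 4, intracluster correlation 0.5, and about 1,080 stores, described as about three times the minimum. The pilot purchase rates are not given, so the minimum cannot be reproduced. What follows from the stated inputs:
- Implied minimum: 1,080 / 3 = 360 stores.
- Design effect: 1 + (4 − 1) × 0.5 = 2.5.
- Effective stores per arm: 180 / 2.5 = 72 at the minimum, and 540 / 2.5 = 216 at 1,080.
- With 85% power, 72 effective stores per arm corresponds to a difference of about 17 to 25 points (pooled-variance formula, no continuity correction, higher rate between 0.30 and 0.95; for example 0.90 against 0.70).

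**2. What is fixed in the encounter and what is left open.**
- Fixed: claim to be an adult and show no proof (Section 5.2); press on price until told the product is the cheapest (Appendix 2, step 8); hold out for cartridges rather than a set (Appendix 2, special situations).
- Open: how many times to ask again, and when to stop, after a refusal or an ID request. Neither Section 5.2 nor Appendix 2 says.

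**3. What is checked.** For formal visits no second observer or recording is described. Coordinators give assistance (Section 9.2), and their waiting outside the store is described only for field training (Section 7.4.2). The two-analyst cleaning in Section 9.3 looks for logical and range errors, which would not reveal a plausible but biased entry. No step compares Question 37 (successful purchase) with the products collected.

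**4. Where judgement enters the form.** Question 26 (dissuasion) calls for interpretation. Question 23 asks whether the buyer was told to leave without sales communication. A yes ends the form before Questions 26 and 37, so an unblinded judgement determines whether those two items are answered at all. Question 37 itself is a plain yes or no about a purchase that leaves a product behind.

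**5. Scale, as an illustration.** The documents give no estimate of any bias, so 2, 5 and 10 points are assumed values.
- Standard error of the difference at a rate of 0.5, where it is largest: √(2 × 0.25 / 216) = 0.048, or 4.8 points.
- Coverage of a 95% interval: Φ(1.96 − k) − Φ(−1.96 − k), with k = bias / SE.
- Chance of a significant result when attire truly has no effect: normal approximation for two proportions, 216 effective stores per arm, base rates 0.3 to 0.9; nominal value 0.05.

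| Assumed bias | k | Coverage | Chance of a significant result, no true effect |
|---|---|---|---|
| 2 points | 0.42 | 93% | 0.07 to 0.10 |
| 5 points | 1.04 | 82% | 0.18 to 0.35 |
| 10 points | 2.08 | 45% | 0.55 to 0.83 |

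The intracluster correlation of 0.5 makes this a mild picture. At an assumed 0.1, the design effect is 1 + 3 × 0.1 = 1.3, the effective size 540 / 1.3 = 415 per arm and the standard error about 3.5 points. Coverage at a 5-point bias is then about 70%.

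**The case against.** Unblinding is inherent in the design and Section 7.1.4 discloses it. Section 7.4.1 names the purpose, not the hypothesis. The primary objective in Section 2.2 is neutrally worded, and Section 8.6 calls the main goal a national description of seller behaviour. A reader might infer that buyers are taught that uniforms reduce sales. No passage says so; it is a possible consequence of explaining the background and purpose.

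A reader might also take the instruction to insist as telling buyers to push against refusals. It concerns only cartridges versus a complete set, and it applies equally to both arms.

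The safeguards are real: scripted answers, role-play, the manual, the 90% threshold, data entry straight after the visit, and new random buyer numbers in each city. The manual is said to cover special situations and standardised communication. It is not reproduced, so a persistence rule could be in it.

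Finally, buyers wear both outfits and record their attire on the form, so many will guess the comparison however they are briefed.

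Most of this stands, and it narrows the point. It does not close it. None of the safeguards is stated to govern what happens after a refusal or an ID request, and none acts on an expectation tied to attire. That buyers may guess the aim limits what a neutral briefing can achieve. It also makes the persistence rule more valuable, since that rule works even when they do guess.

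**Conclusion.** The point holds in a limited form. Expectation could change how long buyers persist in each arm, which would affect the primary outcome, and how they score Questions 23 and 26. Misrecording of Question 37 is a lesser risk: the entry is made soon after the visit and a sale leaves a physical product.

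A reader might conclude that the trial is biased in favour of uniforms by some known amount. The documents do not support that. The likely direction is towards the hypothesis, but a buyer who expects refusal may instead try harder. The size cannot be determined from the documents, and the coverage figures only show what biases of 2, 5 or 10 points would do at a standard error of 4.8 points. If the true effect is as large as the 17 to 25 points implied by the threefold claim, a bias of a few points would distort the estimate more than the conclusion that an effect exists.

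The verdict rests on three assumptions: that explaining the purpose conveys some directional expectation, that the manual contains no persistence rule, and that the plan's intracluster correlation and cluster size apply. The changes are worth making because they are cheap and each removes or limits a route for bias by arm.

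**What to change.** 1. In Section 7.4.1 and Appendix 7, brief buyers with the neutral survey description already used on the poster, present attire as an assigned dress code, and withhold the directional hypothesis until field work ends.
2. In Appendix 2, set one persistence rule for both arms: one explicit purchase request and at most one repeat after a first refusal or ID request, ending at once if asked to leave. Because it is a maximum, it can still be followed when a seller ends the visit early.
3. Have the on-site coordinators reconcile each day's Question 37 answers with the products handed in, by store ID, and log any discrepancy.

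The cost is revised training slides, a line in the script and a short daily check by staff already travelling with each team. The limitation is that masking will be partial, because every buyer wears both outfits. If visits have already been made, reconcile any surviving products or purchase records with Question 37 and report the remaining risk as a limitation.
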